The effects of Remote Microphone Hearing Aids (RMHAs) on classroom listening, listening-in-noise and attention skills in children, aged 7-12, with Auditory Processing Disorder (APD)

(Student Study)

NCT02353091

26/03/20

The research was funded as a PhD studentship by GN Resound (Company sponsor), which also provides the FM systems that will be used in this study, and a UCL Impact award.

Summary

Children with Auditory Processing Disorder (APD) have poor auditory processing skills in the presence of normal peripheral hearing. These children are found to have worse listening-in-noise skills than typically developing peers, while other commonly reported symptoms include poor attention and distractibility. One of the management strategies for children with APD is the use of Remote Microphone Hearing Aids (RMHAs), which can help improve the signal-to-noise ratio in the child's ears. The aim of this randomised control trial was to examine whether RMHA use improves classroom listening for children with APD, and to further test their effects on children's listening-in-noise and attention skills following a 6-month intervention.

The principal research question is whether RMHAs improve classroom listening, listening in noise performance, listening in spatialised noise and auditory attention, in children with Auditory Processing Disorder (APD). We hypothesize that RMHA use will lead to improved classroom listening and improved speech-in-noise skills after 6 months of RMHA use. Additionally, we hypothesise that listening in spatialised noise and attention skills will remain unchanged following the intervention period.

Twenty-six (26) children with a diagnosis of an APD from the Great Ormond Street Hospital Audiology clinic will be recruited. The children need to fulfil the following criteria:

1. Diagnosis of APD based on routine clinical tests, administered by qualified audiologists, and requiring the following conditions:
2. No neurological or pervasive disorder or developmental delay. Children with a diagnosis of Attention Deficit Hyperactivity Disorder, epilepsy, Autism Spectrum Disorder, Developmental Language Disorder, Down Syndrome were excluded from the study.
3. Non-verbal cognitive ability score (IQ) of 85 or more.
4. Aged between 7-12 years.
5. Native English speakers.
6. No prior use of RMHAs.

Background and justification of the study

Auditory Processing Disorder

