Attention and ability to listen in spatialised noise in children with APD after the use of an FM system has been looked at by one uncontrolled study (12). As the central point of this study will be the use of the RMHA by children with APD for 6 months, it is expected that the findings could add valuable information on the subject. In addition, possible benefits of the system will be examined in detail. More particularly, possible long-term improvements in speech in noise performance (unaided), listening in spatialised noise (unaided), and auditory attention (unaided) will be examined.

Listening in noise and attention

A study compared the scores in the Hearing in Noise test of 10 children with APD at baseline unaided and after 5 months of daily RMHA use at school (9). The use of RMHAs during the aided test condition at 5 months gave a gain of approximately 10 dB in the SiN test compared to the unaided testing at baseline, with the authors concluding that RMHA use improved the auditory system in children with APD (9). However, this SiN improvement in the aided condition may reflect an auditory acclimatisation benefit similar to the one reported for hearing aids (13), as there was no significant improvement between pre- and post-intervention in unaided SiN testing. Another APD study used low-gain hearing aids equipped with a directional microphone and noise reduction (14), to examine changes in aided SiN skills in 14

children with APD. They reported improved aided SiN test results¹ after 6 months of RMHA use. Another intervention trial examined the ability to listen in spatial noise² on 28 children with APD who used RMHAs for 5 months (12). Children were tested on two tasks, easy words and hard words, and two conditions, with and without the RMHA at baseline and post-intervention. Results showed a significant improvement only in the easy words task when comparing the unaided with the aided conditions (12). All three trials lacked control groups and randomised designs, thus further validation in controlled trials, especially in unaided conditions, is required.

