Furthermore, to date only one study looked into the long-term impact of RMHAs on behavioural attention tests in children with APD. Specifically, sustained auditory and sustained visual attention was examined in 28 children with APD after a 5-month RMHA intervention, without showing any significant change over the intervention period (12). One other study used the Children's Auditory Performance Scale questionnaire, completed by parents at baseline and after 6 months of using the directional microphone hearing aids at school (14). While the Auditory Attention Span subscale of the questionnaire showed significantly improved scores post-intervention, it still remained below what was considered normal cut-off. Parents observed their children at home, when hearing aids were not used, suggesting that the improvement in the subscale scores may have been due to lasting effects on their attentive behaviours. The findings from these two studies are conflicting, but none of the trials used a randomised control design (14).

Aim and hypotheses

In the present study we aim to test the impact of long-term RMHA use on self-reported listening, behavioural SiN performance and to assess behaviourally whether listening-in-spatialised-noise skills change after prolonged RMHA use and to assess the impact RMHA use has on attention skills.

Research questions:

The principal research question was to examine the effects of RMHAs on classroom listening, listening in noise performance, and auditory attention in children with APD.

Hypotheses:

- i. Children with APD who use RMHAs will show greater improvements in classroom listening, listening in noise and sustained auditory attention (unaided) after 6 months of RMHA use in comparison to the APD control group.

¹ The North Western University word-list was used in combination with speech-shaped noise coming from 180° that was individually adjusted (14).

² Words from the Lexical Neighbourhood Test were presented from the front, while a 100-talker babble recording was presented left, right, and behind the subject (12).

- ii. Children with APD who use the RMHA will not show greater improvements in listening in spatialised speech noise and divided and visual attention measures after 6 months of RMHA use in comparison to the APD control group.

Summary of main issues

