We will recruit 26 children, 7-12 years old. All children will have been diagnosed and referred from the Auditory Processing Disorders Clinic at Great Ormond Street Hospital. The total sample size is decided using this power sample: $N = 24$ (total sample size) calculated using the F test for repeated measures between-within interaction Analysis of Variance (ANOVA) based on an estimated 0.5 effect size $f(U)$, 80% power, at 5% significance, using 2 groups and 3 measurement points. To account for a 10% loss due to follow-up, the total sample size of this study was 26 children, aged 7-12.

Inclusion criteria:

1. Diagnosis of APD based on routine clinical tests, administered by qualified audiologists, and requiring the following conditions:

- a) Reported parental SiN and other reported listening difficulties.
 - b) Normal peripheral hearing and middle ear function; i.e. air conduction PTA below 20 dB in all octave frequencies between 250 Hz and 8 KHz (31), middle-ear pressure between -150 to +50 daPa, middle-ear admittance between 0.3 to 1.6 cm³ and ear-canal volumes between 0.4 to 1.0 cm³ (32).
 - c) Abnormal performance on the Auditory Figure Ground (AFG) SiN test of the SCAN-3 C (i.e. at the 1st percentile score as per UK norms), and
 - d) Abnormal performance (-2 SDs from the normative mean) on at least one auditory processing test (i.e. Frequency Pattern Test [FPT], Dichotic Digits Test [DDT], duration pattern test, Gaps-in-Noise [GiN] or random gap detection pattern tests), or a score of -3 SDs from the normative mean on only one auditory processing test (any test from conditions 'c' and 'd'), and/ or abnormal performance (-2 SDs from the mean) on the Spatial Advantage and Total Advantage/ High-cue Speech Reception Threshold (SRT) subtests of the Listening in Spatialised Noise – Sentences (LiSN-S) test.
2. No neurological or pervasive disorder or developmental delay. Children with a diagnosis of Attention Deficit Hyperactivity Disorder, epilepsy, Autism Spectrum Disorder, Developmental Language Disorder, Down Syndrome were excluded from the study.
 3. Non-verbal cognitive ability score (IQ) of 85 or more.
 4. Aged between 7-12 years.
 5. Native English speakers.
 6. No prior use of RMHAs.

Subjects will be semi-randomly assigned to each of two intervention arms. The two groups will be stratified for age and balanced for sex.

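### The 5% level and 80% power belong to one interaction F test with no outcome attached, while benefit is predicted on two or three outcomes with no primary outcome, success rule or multiplicity rule.

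*Combined protocol and SAP*

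**What the plan says.** All references are to the combined protocol and SAP.

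- **Participants and Recruitment** derives N = 24 from an interaction F test in a repeated-measures ANOVA with f(U) = 0.5, "80% power, at 5% significance, using 2 groups and 3 measurement points". It does not say for which outcome 0.5 was estimated.
- **Summary**, question: "The principal research question is whether RMHAs improve classroom listening, listening in noise performance, listening in spatialised noise and auditory attention". That is four outcomes, listed together.
- **Summary**, predictions: benefit on two outcomes, "RMHA use will lead to improved classroom listening and improved speech-in-noise skills after 6 months of RMHA use", and none on two others, "listening in spatialised noise and attention skills will remain unchanged following the intervention period".
- **Aim and hypotheses**, question: "The principal research question was to examine the effects of RMHAs on classroom listening, listening in noise performance, and auditory attention". That is three outcomes. Hypothesis i also predicts benefit on three: the RMHA group "will show greater improvements in classroom listening, listening in noise and sustained auditory attention (unaided". Hypothesis ii predicts no greater improvement in spatialised noise or in divided and visual attention.
- **The assessment list and Explanation of each test** repeat LIFE-R, TEACH, LiSN-S, CHAPS and CCC-2 at baseline, 3 and 6 months, unranked. LiSN-S is the only noise test, and its stated purpose is spatialised noise.
- **Data analysis** specifies a mixed ANOVA with group and time as factors. It names no outcome, no deciding effect, no success rule and no adjustment for multiple tests. It is written in the past tense.

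**The concern.** An error rate and a power figure mean something only for a stated claim. Here the claim spans several outcomes, and no section says whether one success suffices or all are needed. If one suffices, 5% need not be the error rate of the principal claim. If all are needed, there is no inflation, but 80% need not be the power.

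Two further gaps make this worse. A change in sustained auditory attention would support hypothesis i and contradict the Summary. And listening in noise is predicted to improve, yet the only scheduled noise test is described as measuring the construct that is predicted not to.

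Finally, the hypotheses concern benefit after 6 months, whereas the interaction F test has no direction and responds to a difference at any visit. A reader could not tell which significant result decides the trial.

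**Working it through.** **1. Reproduce the plan's figure.** Inputs from Participants and Recruitment: f(U) = 0.5, k = 2 groups, m = 3 times, alpha 0.05. Sphericity is assumed.

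- Noncentrality = f² × (N − k) × (m − 1) = 0.25 × 22 × 2 = 11 at N = 24.
- Degrees of freedom = (k − 1)(m − 1) = 2 and (N − k)(m − 1) = 44. The critical F is 3.21.
- Power from the noncentral F is 82.6% at N = 24 and 78.4% at N = 22.

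So 24 is the smallest total with equal arms that reaches 80%. It is sound for one test.

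**2. Count the predicted benefits that have a scheduled test.**

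| Source | Predicted to improve | If some scheduled score measures listening in noise | If none does |
|---|---|---|---|
| Summary | classroom listening, speech in noise | 2 | 1 |
| Hypothesis i | classroom listening, listening in noise, sustained auditory attention | 3 | 2 |

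The SCAN-3 C figure-ground test is a speech-in-noise test, but it appears only as an entry criterion.

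**3. If any one success at 5% is enough.** For independent outcomes the chance of at least one false rejection is 1 − 0.95^j:

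- one outcome: 5%
- two: 1 − 0.95² = 9.75%
- three: 1 − 0.95³ = 14.3%

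Correlation lowers this. Simulation with 12 per arm and an assumed correlation of 0.5 between outcomes gives about 9.3% (two) and 12.8% (three). At 0.8 it gives about 8% and 10%. The documents give no correlation. Testing subscales, CHAPS or CCC-2 as well would raise the figures.

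**4. If all must succeed.** With f(U) = 0.5 assumed for every outcome, power for independent outcomes is 82.6% (one), 0.826² = 68% (two) or 0.826³ = 56% (three). At an assumed correlation of 0.5 it is about 72% (two) and 65% (three).

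**5. What the F test responds to.** Under sphericity its power depends only on the total noncentrality of 11, not on when the difference appears. Any pattern scaled to f(U) = 0.5 is therefore significant in about 83% of trials, including one present only at 3 months.

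The baseline-to-6-month contrast takes a share of that noncentrality. For group differences d0, d3 and d6 at 0, 3 and 6 months, the share is [(d6 − d0)²/2] ÷ Σ(d − mean d)². The t noncentrality is √(11 × share).

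| Difference at 0, 3, 6 months | Share | t noncentrality | F alone | 6-month contrast alone | Both required |
|---|---|---|---|---|---|
| 0, 0.5, 1 | 1 | 3.32 | 83% | about 89% | about 81% to 82% |
| 0, 1, 1 | 0.75 | 2.87 | 83% | about 79% | about 74% |
| 0, 0, 1 | 0.75 | 2.87 | 83% | about 79% | about 74% |
| 0, 1, 0 | 0 | 0 | 83% | about 2.5% | about 2.4% |

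The contrast is two-sided at 5% and counted only when it favours RMHA. The 79% is 78% with 22 error degrees of freedom (change scores) and 80% with 44 (the pooled interaction error). The last column is simulated.

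**The case against.** The strongest reply is that the Summary does rank the outcomes. The aim is "to examine whether RMHA use improves classroom listening for children with APD, and to further test their effects" on listening in noise and attention, so classroom listening leads. If listening in noise also has no scheduled test, the Summary leaves exactly one testable predicted benefit, and 5% and 83% are then correct as they stand. Part of this holds: inflation is not certain, which is why the range starts at 5%. But the aim never calls classroom listening primary, the sample size is not tied to it, and the question in the same Summary lists it beside three others. Hypothesis i still leaves at least two testable benefits.

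Four stronger readings are tempting, and the documents do not support them:

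- **LiSN-S must be the listening-in-noise measure.** Its stated purpose is spatialised noise only. Assigning it to the other hypothesis could put an instrument predicted to show no benefit into a confirmatory benefit test.
- **Four outcomes, 1 − 0.95⁴ = 18.5%, as the ceiling.** No benefit is predicted for spatialised noise, and the repeated tests include subscales, CHAPS and CCC-2. So 18.5% is neither the expected figure nor an upper bound.
- **Other sections drop classroom listening.** The background says "possible long-term improvements in speech in noise performance (unaided), listening in spatialised noise (unaided), and auditory attention (unaided) will be examined", and Summary of main issues has a similar list. Both are narrative lists about unaided skills and show no competing choice of primary outcome.
- **The sample size is wrong.** It reproduces for one test.

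That this is a small student study does not remove the point: it is a randomised trial with a stated alpha, stated power and directional hypotheses.

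**Conclusion.** The point holds in a limited form. The stated 5% and 80% are attached to no outcome and to no rule for success, and the Summary and hypothesis i contradict each other on attention. Those are findings on the text and need no assumption.

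Their size depends on what the authors meant. The false-rejection chance runs from 5% to 14.3% if any one success counts. Power runs from 83% down to 56% if all must succeed. Both ranges assume independent outcomes and sphericity, and the power range also assumes the same f(U) for each outcome. Neither success rule is stated, so it would go too far to say that the trial has a 14.3% error rate or 56% power.

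Separately, the omnibus F test does not test the 6-month hypothesis, since a difference of the sized magnitude at 3 months alone is significant in about 83% of trials. This should be put right, and it can be done in the text.

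**What to change.** 1. **Reconcile the outcomes.** Make the Summary and Aim and hypotheses agree on the outcome list and on attention. State which scheduled test and score, if any, measures listening in noise. If none does, withdraw that confirmatory hypothesis.
2. **If the data had been analysed**, as the past tense of Data analysis suggests, apply Holm at 5% across the reconciled predicted-benefit outcomes, or disclose any primary outcome as chosen post hoc.
3. **If they had not**, name one primary outcome in Data analysis. LIFE-R for classroom listening is an inference from the order of the aim and from the self-reported listening named under Aim and hypotheses, so the authors must confirm it. Decide the outcome by the baseline-to-6-month group contrast with a two-sided 95% confidence interval. Test the other predicted-benefit outcomes only if it succeeds, with Holm, and label all other scores exploratory.
4. **In Participants and Recruitment**, state the outcome for which f(U) = 0.5 was estimated and restate the power for the deciding test. At N = 24 the contrast has about 89% for a steadily growing benefit, and about 79% for one complete by 3 months or appearing only at 6. If a significant F is also required, the figures are about 81% to 82% and 74%.

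**Cost.** Text only: no added children, visits or tests, and enrolment should not be increased for this. Secondary outcomes face a stricter threshold. At the first Holm step the sized F test has 73.8% power per outcome for two outcomes and 68.1% for three. Power for the primary contrast may sit slightly below 80%, and a primary outcome named after analysis carries less weight.

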Research suggests that children with APD after a prolonged use of RMHAs benefit from improved speech perception which is possibly linked to an enhanced auditory system (9). Adding to that, children with APD have shown improved speech in noise perception when using RMHAs (in an uncontrolled study); hence emphasizing the advantages of RMHAs in discriminating speech in background noise (9). There are not many studies, though, that focus on the use of RMHAs on children with APD.

This study will assess the effects of RMHA use on a range of outcome measures. As the central point of this study will be the use of RMHAs by children with APD for 6 months, it is expected that the findings could add valuable information on the matter. In addition, possible benefits of RMHAs will be examined in detail. More particularly, possible improvements in auditory attention, listening in spatialised noise and speech in noise discrimination (unaided) will be looked into.

Intervention ethical issues:

We will split the children with APD into (a) children who will only receive the RMHA, (b) children who will not receive any intervention for the study period (this group will receive the RMHA after we complete the study, at 6 months under this conditions: The recommendations by the APD clinic at GOSH include RMHA use as management strategies.

Currently from an audit conducted at GOSH APD Clinic, only 1 in 3 children who are recommended to have a RMHA obtain this by school funding (or by their parents funding the device) and this takes place several months after the recommendation has been made. Therefore, provision of this device is not standard practice. As such RMHAs are issued as part of this research study under the condition mentioned above.

An inclusion of a control, no intervention group, is essential for the Randomised Control Trial design we follow.

School and teacher involvement:

The teachers of the children who receive the FM systems will be provided with an information sheet and consent form and will be required to wear the microphone (which picks up the teacher's voice and transmits it wirelessly to the ear receivers in the child's ear) for the duration of the class. Remote microphone hearing aids are provided (funded by the school budget) to some children after clinical recommendations and this is not an unusual situation within the school environment.

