We will liaise with the teacher as well as the Special Educational Needs Co-ordinator (SENCO) of the school in order to ensure that the school will be aware that the student has been issued with the RMHA. A general guide for the system will be made available in addition to information conveyed by the Research Fellow (PhD student) who will visit the school once per term.

Informed consent:

The child's parents will be given detailed written information and consent forms to sign about taking part in the study. They will be given up to a week to study and decide whether they wish for their child to participate in the study. They will only be allowed to take part once they have understood the purpose and procedures of the study and they have signed the consent forms. In addition, children will also be given information sheets adjusted to their age. Written assent from the children in the presence of their parents or carers will be sought.

Rights to withdraw from the study:

This will be outlined on both the information sheet and consent form and explained verbally throughout. This information will state that participants will be allowed to withdraw from the study at any point should they wish to do so. Withdrawal from the study will not involve any penalty or loss of benefit to them –this information is clearly underlined at the information sheet and will be made clear to them verbally.

Data protection:

The parents of the participant and the participant will be informed that their information will be anonymised and kept confidential. Data will be anonymised prior to analysis by the use of participant codes. Storage of the data will be within a secure password protected database and locked filing unit within UCL, in accordance with the data protection act 1998. If withdrawals take place the participants' data will be deleted.

Research Design and Methodology

Participants and Recruitment

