Children will be given RMHAs to use at school and will be compared to the control (no intervention) group. Children will be enrolled in the study for 6 months. All groups will be tested before the start of the RMHA intervention, after 3 months, and at the end of the study (after 6 months of use of the interventions).

Following are the assessments to be performed for both groups at UCL Ear Institute (detailed explanation of these tests is given later):

- Baseline (before recruitment, 0 months into the study):
 - Pure Audiometry Test (PTA)
 - Non-verbal IQ test (Wechsler test of Non-verbal intelligence)
 - Children Questionnaires (LIFE-R)
 - Attention test (TEACH)
 - Listening in Spatialised noise (LiSN-S)
 - Questionnaires (CHAPS, CCC-2)
- At 3 months

- Children Questionnaires (LIFE-R)
- Attention test (TEACH)
- Listening in Spatialised noise (LiSN-S)
- Questionnaires (CHAPS, CCC-2)
- At the end of the study (6 months later):
 - Children Questionnaires (LIFE-R)
 - Attention test (TEACH)
 - Listening in Spatialised noise (LiSN-S)
 - Questionnaires (CHAPS, CCC-2)

Explanation of each test:

1. A hearing test (Pure Tone Audiometry approx. 10mins). To determine their hearing is normal.
2. Non-verbal IQ test (Weschler test of non-verbal intelligence). To be performed by the PhD Student. (approx. 15mins). To assess determine whether their intelligence level is above normal.
3. Listening in spatialised noise test (LiSN-S, approx. 15mins). To be administered through the use of headphones by the PhD student. To determine their listening in spatialised speech noise abilities.
4. An attention test. The Test of Everyday Attention for Children (TEACH). To be conducted as play type activities by the PhD student after receiving sufficient training by the clinical psychologist. (approx. 45mins possibly cut down to 30mins). To assess their attention.
5. Two questionnaires to be filled by the children's parents.
 - a. The Children's Communication Checklist-2 (CCC-2). A 70-item questionnaire which screens for communication problems (including language disorders and autism).
 - b. The Children's Auditory Performance Scale (CHAPS). It assesses aspects of children's listening.
6. One questionnaire to be completed by the children (Listening Inventory For Education-Revised [LIFE-R] for assessing their listening difficulty.

Data analysis:

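### Allocation is described as 'semi-random' in a trial labelled randomised: the procedure is never stated, and the analysis omits age and sex, the factors used to form the arms

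*Combined protocol and SAP*

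**What the plan says.** How the arms are formed is stated once, at the end of the inclusion criteria in Participants and Recruitment: "Subjects will be semi-randomly assigned to each of two intervention arms. The two groups will be stratified for age and balanced for sex". Intervention ethical issues adds only that the children are split into two groups. There is no definition of the term, no method of generating a sequence, and no age bands, block size, minimisation rule, concealment or named allocator.

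The design label is firmer. The Summary says "The aim of this randomised control trial was to examine whether RMHA use improves classroom listening for children with APD", and Intervention ethical issues says "An inclusion of a control, no intervention group, is essential for the Randomised Control Trial design we follow". The section Listening in noise and attention uses randomisation to justify the trial. Of earlier intervention studies it says "All three trials lacked control groups and randomised designs", and of the two studies on attention, "none of the trials used a randomised control design".

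Data analysis gives one model: a mixed ANOVA with group (two levels) and time (three levels). Age and sex are not in it.

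**The concern.** Randomisation restricted by age and sex is still randomisation. Placement by an investigator who evens out the groups is not, even if the arms end up matched on age and sex. The wording allows either, and the prefix 'semi' qualifies the randomness itself.

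What is at stake is the advance claimed over earlier uncontrolled studies. Under restricted randomisation, that advance holds. Under placement by hand, the arms could differ in expected change for reasons other than age and sex. The group-by-time test could not separate such a difference from a device effect, and age and sex terms would not remove it.

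The second matter is smaller. The arms are formed using age and sex, but the model ignores both. If either predicts change over the 6 months, that variation stays in the error term.

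**Working it through.** **Allocation: the passages side by side**

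1. The Summary and Intervention ethical issues state a randomised design. Participants and Recruitment states semi-random assignment with stratification and balancing. No other section gives a procedure that would reconcile them.
2. The order of events does not settle it. Informed consent lets children take part only "once they have understood the purpose and procedures of the study and they have signed the consent forms". The schedule says "All groups will be tested before the start of the RMHA intervention" and labels the first visit "Baseline (before recruitment, 0 months into the study". Read literally, that label puts testing ahead of recruitment, which sits awkwardly with the consent rule. None of these statements says when the arm is assigned or disclosed, or how it is chosen.
3. Tenses are mixed. Assignment is in the future tense, but the aim, the sample size, the exclusions and the data analysis are in the past tense, and the document is dated 26/03/20. Completed allocation is the likelier reading.

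**Analysis: the plan's own figure**

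Inputs from Participants and Recruitment: f(U) = 0.5, 80% power, 5% significance, 2 groups, 3 time points, N = 24. Sphericity is assumed.

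- Noncentrality λ = f² × (N − 2) × (3 − 1). At N = 24, λ = 0.25 × 22 × 2 = 11.
- Degrees of freedom: 2 and 2 × 22 = 44.
- Power is 0.826 at N = 24 and 0.784 at N = 22, so 24 is the smallest even total above 80%. The stated figure reproduces.

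**Adding age and sex**

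With age in two bands, age-by-time and sex-by-time use 2 error degrees of freedom each, so 44 − 4 = 40. With λ = 11 and F(2, 40), power is 0.823. If age and sex predict nothing, the loss is 0.826 − 0.823 = 0.003.

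**Leaving age out when it predicts change**

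Assumptions, none from the documents: four age-by-sex cells of 6 children with 3 per arm; a linear age-by-time effect; R² is the share of 0 to 6 month change variance explained by age; f(U) = 0.5 is relative to the within-child error left once age is removed.

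Let σ² be that error variance. Change variance from error is 2σ², so an age effect of ±a on change satisfies a² = 2σ²R²/(1 − R²). The linear pattern contributes 24 × a²/2 to the unadjusted error sum of squares:

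- R² = 0.10: a² = 0.222σ², added sum of squares 2.67σ², error mean square (44 + 2.67)/44 = 1.06σ².
- R² = 0.30: a² = 0.857σ², added sum of squares 10.29σ², error mean square (44 + 10.29)/44 = 1.23σ².

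The group-by-time sum of squares is unaffected because age is balanced across arms. The F ratio is therefore too small, and the test is conservative. Simulation gives:

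| R² (assumed) | Power without age and sex | Power with | Type I error without | Type I error with |
|---|---|---|---|---|
| 0 | 0.83 | 0.82 | 0.05 | 0.05 |
| 0.10 | 0.80 | 0.82 | about 0.04 | 0.05 |
| 0.30 | 0.74 | 0.82 | about 0.026 | 0.05 |

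Results were nearly the same for a treatment effect growing linearly and for one fully present from 3 months.

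**The case against.** The strongest reply is that this is one undefined word. The documents twice state a randomised design, and stratifying and balancing are ordinary terms for restricted randomisation. Nothing positively indicates placement by hand. This stands as far as it goes: the benign reading is available and may be the more natural one. It does not make the procedure known.

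A reader might go further and infer that the trial was not randomised, or that its false-positive rate is inflated by a known amount. The documents support neither. A rate can be produced only by assuming how far the arms differ in untreated change. At N = 24, an assumed difference of 0.1 SD of that change gives 0.054 to 0.056, and 0.5 SD gives 0.17 to 0.21, against a nominal 0.05. The documents supply no such difference, so these rates are not evidence of bias.

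It is also fair to say that a new sequence is of little use if allocation is over. That stands, and it sets the order of the remedies.

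On age and sex, the reply is that leaving them out is defensible: constant effects cancel in the group-by-time test, and under balanced random allocation the omission creates no excess false positives. That also stands. But the test becomes conservative if age or sex predicts change, and including them costs almost nothing.

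**Conclusion.** The concern holds as a gap between label and description. The wording is compatible with restricted randomisation but does not exclude placement by hand, and the randomised label is secure only under the first. Whether any bias exists, and its size, cannot be determined from the documents.

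The omission of age and sex is a secondary matter of power, not validity. The cost of including them, 0.003 in power, follows from the plan's own inputs under sphericity with age in two bands. The gain, from about 0.80 to 0.74 up to 0.82, rests on the assumed 10 to 30% of change variance explained by age and on balanced cells. Adjustment would not repair non-random allocation.

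**What to change.** **If allocation is complete, as the text suggests:** replace the allocation sentence with the procedure actually used. Say how assignments were generated, which age bands were used, how sex was balanced, who assigned, and whether the arm was known before consent and baseline testing. If the procedure was not random, call the study a non-randomised controlled trial throughout and limit its conclusions accordingly. This costs a few sentences and leaves the sample size unchanged.

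**Only if allocation is still ahead:** replace 'semi-randomly' with a concealed computer-generated sequence stratified by age band and sex, or minimisation with a random element. Disclose the arm after consent and baseline testing. Someone other than the PhD student who administers the tests should hold the sequence; the documents name no such person.

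**Analysis:** if the data are not yet analysed, add age and sex, each with its interaction with time, to the mixed ANOVA. If they have been analysed, keep the stated model as the main analysis and report the extended one as a labelled sensitivity analysis, at the cost of one extra run.
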